10.10.7. Efficacy Figures

| Efficacy: Figures | | | | | |
|---|------------|----------------------|--|---------------------------------------|-------------|
| No. | Population | IDSL / Example Shell | Title | Programming Notes | Deliverable |
| Primary Efficacy Analyses: Model based Mean Change in Hgb between Baseline and Evaluation Period | | | | | |
| 2.1. | ITT | EFF_F1 | Line Plot of Post-randomization Observed and Imputed Hemoglobin Data by Visit | | DR, SAC |
| 2.2. | ITT | EFF_F1 | Line Plot of Post-randomization Observed and Imputed Hemoglobin Change from Baseline | | DR, SAC |
| Principal Secondary Efficacy Analyses | | | | | |
| 2.3. | ITT | EFF_F1 | Line Plot of On-Treatment Observed and Imputed SF-36 vitality sub-score values by Visit, Traditional Scoring | | DR, SAC |
| 2.4. | ITT | EFF_F1 | Line Plot of On-Treatment Observed and Imputed SF-36 vitality sub-score values Change from Baseline | | DR, SAC |
| Secondary Efficacy Statistical Analyses: Symptom Severity and Change | | | | | |
| 2.5. | ITT | EFF_F3 | Bar Chart of On-treatment Baseline and CKD-AQ Domain and Single Item Scores by Visit | Page by domain and single item scores | DR, SAC |
| 2.6. | ITT | EFF_F4 | Stacked Bar Chart of On-treatment Baseline and Week 28 Scores for PGI-S Response | | DR, SAC |
| Secondary Efficacy Statistical Analyses: HRQoL and Utility score | | | | | |
| 2.7. | ITT | EFF_F3 | Bar Chart of On-treatment SF-36 individual items of the Vitality Domain Scores Change from Baseline | Page by individual items | DR, SAC |
| 2.8. | ITT | EFF_F3 | Line Plot of On-treatment SF-36 Physical Function Domain Scores Change from Baseline | | SAC |

CONFIDENTIAL

205270

| Efficacy: Figures | | | | | |
|---|------------|----------------------|---|-------------------|-------------|
| No. | Population | IDSL / Example Shell | Title | Programming Notes | Deliverable |
| 2.9. | ITT | EFF_F3 | Bar Chart of On-treatment EQ-5D-5L Scores by Visit | | DR, SAC |
| Exploratory Efficacy Statistical Analyses: Iron Parameters | | | | | |
| 2.10. | ITT | EFF_F1 | Line Plot of On-treatment Hepcidin Data by Visit | | DR, SAC |
| 2.11. | ITT | EFF_F1 | Line Plot of On-treatment Hepcidin Percent Change from Baseline | | DR, SAC |
| 2.12. | ITT | EFF_F1 | Line Plot of On-treatment TSAT Data by Visit | | DR, SAC |
| 2.13. | ITT | EFF_F1 | Line Plot of On-treatment TSAT Change from Baseline | | DR, SAC |
| 2.14. | ITT | EFF_F1 | Line Plot of On-treatment Ferritin Data by Visit | | DR, SAC |
| 2.15. | ITT | EFF_F1 | Line Plot of On-treatment Ferritin Percent Change from Baseline | | DR, SAC |
| 2.16. | ITT | EFF_F1 | Line Plot of On-treatment Serum Iron Data by Visit | | DR, SAC |
| 2.17. | ITT | EFF_F1 | Line Plot of On-treatment Serum Iron Percent Change from Baseline | | DR, SAC |
| 2.18. | ITT | EFF_F1 | Line Plot of On-treatment TIBC Data by Visit | | DR, SAC |
| 2.19. | ITT | EFF_F1 | Line Plot of On-treatment TIBC Change from Baseline | | DR, SAC |
| Exploratory Efficacy Statistical Analyses: Renal | | | | | |
| 2.20. | ITT | EFF_F1 | Line Plot of On-treatment eGFR Data by Visit | | DR, SAC |
| 2.21. | ITT | EFF_F1 | Line Plot of On-treatment eGFR Change from Baseline | | DR, SAC |
| 2.22. | ITT | EFF_F1 | Line Plot of On-treatment Serum Creatinine Data by Visit | | DR, SAC |
| 2.23. | ITT | EFF_F1 | Line Plot of On-treatment Serum Creatinine Change from Baseline | | DR, SAC |

CONFIDENTIAL

205270

| Efficacy: Figures | | | | | |
|--|------------|----------------------|--|-------------------|-------------|
| No. | Population | IDSL / Example Shell | Title | Programming Notes | Deliverable |
| Exploratory Efficacy Statistical Analyses: Dose Adjustment Scheme | | | | | |
| 2.24. | ITT | EFF_F5 | Stacked Bar Chart of Assigned Daprodustat Dose by Visit | | SAC |
| Additional Efficacy Figures | | | | | |
| 2.25. | ITT | EFF_F4 | Stacked Bar Chart of On-treatment Baseline and Week 28 Scores for PGI-C Response | | SAC |

10.10.8. Safety Tables

| Safety: Tables | | | | | |
|-----------------------------|------------|----------------------|---|--|-------------|
| No. | Population | IDSL / Example Shell | Title | Programming Notes | Deliverable |
| Adverse Events (AEs) | | | | | |
| 3.1. | Safety | Shell 32 | Summary of All Treatment Emergent Adverse Events by System Organ Class and Preferred Term | ICH E3 Add exposure-adjusted AE incidence for both treatments | DR, SAC |
| 3.2. | Safety | Shell 32 | Summary of All Treatment Emergent Adverse Events by System Organ Class, Higher Level Term, and Preferred Term | ICH E3 | DR, SAC |
| 3.3. | Safety | Shell 32 | Summary of All Follow-Up Adverse Events by System Organ Class and Preferred Term | ICH E3 | DR, SAC |
| 3.4. | Safety | Shell 33 | Summary of Common ($\geq 5\%$) Treatment Emergent Adverse Events by Overall Frequency | ICH E3 | DR, SAC |

CONFIDENTIAL

205270

| Safety: Tables | | | | | |
|-----------------------|-------------------|-----------------------------|--|----------------------------|--------------------|
| No. | Population | IDSL / Example Shell | Title | Programming Notes | Deliverable |
| 3.5. | Safety | Shell 32.1 | Summary of All Treatment Emergent Adverse Events by Maximum Intensity by System Organ Class and Preferred Term | ICH E3 | DR, SAC |
| 3.6. | Safety | Shell 32 | Summary of All Drug-Related Treatment Emergent Adverse Events by System Organ Class and Preferred Term | ICH E3 | DR, SAC |
| 3.7. | Safety | Shell 32 | Summary of All Serious Drug-Related Treatment Emergent Adverse Events by System Organ Class and Preferred Term | | DR, SAC |
| 3.8. | Safety | AE20 | Summary of Treatment Emergent Serious Fatal and Non-Fatal Drug-Related Adverse Events by Overall Frequency | Page by fatal vs non-fatal | DR, SAC |
| 3.9. | Safety | Shell 32 | Summary of All Non-Serious Drug-Related Treatment Emergent Adverse Events by System Organ Class and Preferred Term | | DR, SAC |
| 3.10. | Safety | Shell 33 | Summary of All Non-Serious Drug-Related Treatment Emergent Adverse Events by Overall Frequency | | DR, SAC |
| 3.11. | Safety | Shell 34 | Summary of Common ($\geq 5\%$) Non-serious Treatment Emergent Adverse Events by System Organ Class and Preferred Term (Number of Subjects and Occurrences) | FDAAA, EudraCT | DR, SAC |
| 3.12. | Safety | Shell 32.1 | Summary of All Treatment Emergent Drug-Related Adverse Events by System Organ Class and Preferred Term and Maximum Intensity | ICH E3 | DR, SAC |
| 3.13. | Safety | Shell 32 | Summary of All Treatment Emergent Adverse Events by System Organ Class and Preferred Term by Race | | DR, SAC |
| 3.14. | Safety | Shell 32 | Summary of All Treatment Emergent Adverse Events by System Organ Class and Preferred Term by Age | | DR, SAC |
| 3.15. | Safety | Shell 32 | Summary of All Treatment Emergent Adverse Events by System Organ Class and Preferred Term by Gender | | DR, SAC |

CONFIDENTIAL

205270

| Safety: Tables | | | | | |
|---|------------|----------------------|---|--|-------------|
| No. | Population | IDSL / Example Shell | Title | Programming Notes | Deliverable |
| 3.16. | Safety | Shell 49 | Summary of Treatment Emergent Adverse Events of Special Interest by Preferred Term | Add exposure-adjusted AE incidence for both treatments | DR, SAC |
| 3.17. | ITT | Shell 1 | Summary of First-Occurrence of Adjudicated MACE | | DR, SAC |
| 3.18. | ITT | Shell 3 | Summary of All Adjudicated MACE | | DR, SAC |
| 3.19. | ITT | Shell 1 | Summary of First Occurrence of Adjudicated MACE or Thromboembolic Events or Hospitalization for Heart Failure | | DR, SAC |
| 3.20. | ITT | Shell 3 | Summary of All Adjudicated MACE or Thromboembolic Events or Hospitalization for Heart Failure | | DR, SAC |
| Serious and Other Significant Adverse Events | | | | | |
| 3.21. | Safety | Shell 34 | Summary of Serious Treatment Emergent Adverse Events by System Organ Class and Preferred Term (Number of Subjects and Occurrences) | FDAAA, EudraCT | DR, SAC |
| 3.22. | Safety | Shell 32 | Summary of Serious Treatment Emergent Adverse Events by System Organ Class, Higher Level Term, and Preferred Term | ICH E3 | DR, SAC |
| 3.23. | Safety | Shell 34 | Summary of Serious Follow-Up Adverse Events by System Organ Class and Preferred Term (Number of Subjects and Occurrences) | FDAAA, EudraCT | DR, SAC |
| 3.24. | Safety | Shell 32 | Summary of Treatment Emergent Adverse Events Leading to Permanent Discontinuation of Study Treatment by System Organ Class and Preferred Term | IDSL Add exposure-adjusted AE incidence for both treatments | DR, SAC |
| Laboratory: Chemistry | | | | | |
| 3.25. | Safety | Shell 16 | Summary of Post-randomization Chemistry Change from Baseline | ICH E3 | DR, SAC |
| 3.26. | Safety | Shell 36 | Summary of Worst Case On-treatment Chemistry Results PCI Criteria Post-Baseline Relative to Baseline | ICH E3 | DR, SAC |

CONFIDENTIAL

205270

| Safety: Tables | | | | | |
|--|-------------------|-----------------------------|---|--------------------------|--------------------|
| No. | Population | IDSL / Example Shell | Title | Programming Notes | Deliverable |
| 3.27. | Safety | Shell 35 | Summary of Worst Case On-treatment Chemistry Results Relative to Normal Range Post-Baseline Relative to Baseline | ICH E3 | DR, SAC |
| Laboratory: Hematology | | | | | |
| 3.28. | Safety | Shell 16 | Summary of Post-randomization Hematology Change from Baseline | ICH E3 | DR, SAC |
| 3.29. | Safety | Shell 36 | Summary of Worst Case On-treatment Hematology Results by PCI Criteria Post-Baseline Relative to Baseline | ICH E3 | DR, SAC |
| 3.30. | Safety | Shell 35 | Summary of Worst Case On-treatment Hematology Results Relative to Normal Range Post-Baseline Relative to Baseline | ICH E3 | DR, SAC |
| Laboratory: Hepatobiliary (Liver) | | | | | |
| 3.31. | Safety | Shell 37 | Summary of Post-randomization Liver Monitoring/Stopping Event Reporting | IDSL | DR, SAC |
| 3.32. | Safety | Shell 38 | Summary of Post-randomization Hepatobiliary Laboratory Abnormalities | IDSL | DR, SAC |
| Vital Signs | | | | | |
| 3.33. | Safety | Shell 15 | Summary of Post-randomization Vital Signs by Visit | ICH E3 | DR, SAC |
| 3.34. | Safety | Shell 16 | Summary of Post-randomization Change from Baseline in Vital Signs by Visit | ICH E3 | DR, SAC |
| 3.35. | Safety | Shell 36 | Summary of Worst Case On-treatment Vital Sign Results Relative to Potential Clinical Importance (PCI) Criteria Post-Baseline Relative to Baseline | IDSL | DR, SAC |
| Other Safety Tables | | | | | |
| 3.36. | Safety | PAN1 | Summary of COVID-19 Assessment | No events column | SAC |

CONFIDENTIAL

205270

| Safety: Tables | | | | | |
|----------------|------------|----------------------|---|--|-------------|
| No. | Population | IDSL / Example Shell | Title | Programming Notes | Deliverable |
| 3.37. | Safety | PAN10 | Summary of Exposure Adjusted Incidence Rates Over Time | - Timeblock 1= pre-pandemic - Timeblock 2= during-pandemic | SAC |
| 3.38. | Safety | PAN10 | Summary of Exposure Adjusted Incidence Rates Over Time by Region | - Timeblock 1= pre-pandemic - Timeblock 2= during-pandemic | SAC |
| 3.39. | Safety | PAN10 | Summary of Exposure Adjusted Incidence Rates Over Time by Age | - Timeblock 1= pre-pandemic - Timeblock 2= during-pandemic | SAC |
| 3.40. | Safety | PAN10 | Summary of Exposure Adjusted Incidence Rates Over Time by Gender | - Timeblock 1= pre-pandemic - Timeblock 2= during-pandemic | SAC |
| 3.41. | Safety | PAN11 | Summary of Exposure Adjusted Incidence Rate for Common (>=5%) Adverse Events | - Timeblock 1= pre-pandemic - Timeblock 2= during-pandemic | SAC |
| 3.42. | Safety | Shell 15 | Summary of Post-randomization Chemistry by Visit | | SAC |
| 3.43. | Safety | Shell 15 | Summary of Post-randomization Hematology by Visit | | SAC |
| 3.44. | Safety | Shell 32 | Summary of All Treatment Emergent Serious Adverse Events by System Organ Class and Preferred Term | ICH E3 Add exposure-adjusted AE incidence for both treatments | SAC |
| 3.45. | Safety | Shell 32 | Summary of Treatment Emergent Fatal Adverse Events by System Organ Class and Preferred Term | Add exposure-adjusted AE incidence for both treatments | SAC |
| 3.46. | Safety | Shell 32 | Summary of All Treatment Emergent Adverse Events by System Organ Class and Preferred Term by Weight Quartile | | SAC |
| 3.47. | Safety | Shell 50 | Summary of Characteristics of Treatment Emergent Adverse Event of Special Interest of Death, Myocardial Infarction, Stroke, Heart Failure, Thromboembolic Events, and Thrombosis of Vascular Access | | SAC |

CONFIDENTIAL

205270

| Safety: Tables | | | | | |
|-----------------------|-------------------|---------------------------------|---|--------------------------|--------------------|
| No. | Population | IDSL / Example Shell | Title | Programming Notes | Deliverable |
| 3.48. | Safety | Shell 50 | Summary of Characteristics of Treatment Emergent Adverse Event of Special Interest of Thrombosis and/or Tissue Ischemia Secondary to Excessive Erythropoiesis | | SAC |
| 3.49. | Safety | Shell 50 | Summary of Characteristics of Treatment Emergent Adverse Event of Special Interest of Cardiomyopathy | | SAC |
| 3.50. | Safety | Shell 50 | Summary of Characteristics of Treatment Emergent Adverse Event of Special Interest of Pulmonary Artery Hypertension | | SAC |
| 3.51. | Safety | Shell 50 | Summary of Characteristics of Treatment Emergent Adverse Event of Special Interest of Cancer-related Mortality and Tumor Progression and Recurrence | | SAC |
| 3.52. | Safety | Shell 50 | Summary of Characteristics of Treatment Emergent Adverse Event of Special Interest of Esophageal and Gastric Erosions | | SAC |
| 3.53. | Safety | Shell 50 | Summary of Characteristics of Treatment Emergent Adverse Event of Special Interest of Proliferative Retinopathy, Macular Edema, Choroidal Neovascularization | | SAC |
| 3.54. | Safety | Shell 50 | Summary of Characteristics of Treatment Emergent Adverse Event of Special Interest of Exacerbation of Rheumatoid Arthritis | | SAC |
| 3.55. | Safety | Shell 50 | Summary of Characteristics of Treatment Emergent Adverse Event of Special Interest of Worsening of Hypertension | | SAC |

CONFIDENTIAL

205270

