7.7.2. Rescue Criteria

A rescue algorithm is provided to minimize participants having an inadequate response to the treatment for their anemia for an extended period of time and to enable consistency in the application of rescue therapy across the study. Details are provided in [Table 7](#).

This rescue algorithm **does not** apply to participants with low Hgb as a result of an acute or subacute event with an identifiable cause (e.g., GI bleed, blood loss due to surgery or vascular access). In these cases, treatment should be directed to the specific cause and randomized treatment will be continued at the current dose (unless Hgb is ≥ 13 g/dL which requires a dose hold).

Table 7 Rescue Algorithm for Anemia Management

Evaluate Participant for Rescue starting from Week 4 if:	

 • HemoCue Hgb is <7.5g/dL, or • HemoCue Hgb is <8.5g/dL and participant is symptomatic¹, or • HemoCue Hgb is <8.5 g/dL on three consecutive visits 	
Step 1: Initial Intervention	
Initial intervention depends on the participant's iron status:
 
 • If participant has TSAT < 15% and/or Ferritin < 50 ng/mL from a prior study visit, then 
 ○ continue with study treatment, and ○ intervene with iron therapy: Single dose of IV iron up to 1000 mg (in addition to the iron management criteria) 
At the next study visit in 4 ±1 weeks, recheck HemoCue Hgb. If HemoCue Hgb value continues to meet the evaluation criteria for rescue, then Proceed to Step 2.
 
 • If participant has TSAT ≥15% and Ferritin ≥ 50ng/mL, proceed to step 2.
Step 2: Rescue	
Randomized treatment should be permanently discontinued (but participant should remain in study to monitor Hgb) and the participant should be rescued according to local clinical practice:
 
 • If HemoCue Hgb remains <8.5 g/dL despite Initial Intervention (Step 1) based on the average of two HemoCue Hgb values ² • Rescue can be considered IV iron, rhEPOs and/or Transfusions.

1. Symptoms should be related to anemia of CKD. Further information regarding collecting this data will be stated in the SRM.

2. Repeat HemoCue Hgb at the same study visit to confirm Hgb (using the same sample); take average of 2 values.

The study site will supply any rescue medication that will be obtained locally.

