- For the MMRM analysis of change from baseline in Hgb, an LSMEANS statement will provide adjusted treatment group means and standard errors and a point estimate and two-sided 95% confidence interval for the adjusted mean treatment difference (daprodustat - placebo) at Week 28. The one-sided non-inferiority p-value for this test will be calculated.

Model Results Interpretation

- For the responder analysis, the one-sided CMH p-value will be compared to 0.025 to assess nominal significance.
- For the percent time in range analysis, a nominal superiority will be achieved if the lower limit of the two-sided 95% CI is above 0 and the one-sided p-value is < 0.025
- For the MMRM analysis of change from baseline in Hgb, superiority will be achieved if the lower limit of the two-sided 95% CI is above 0 and the one-sided p-value is < 0.025

Time to Rescue

| |
|---|
| Secondary Efficacy Statistical Analyses: Time to Rescue |
| Endpoint / Variables |
| 
 Time to stopping study treatment due to meeting rescue criteria |
| Model Specification |
| 
 The Cox Proportional Hazards model will adjust for the following baseline categorical values: 
 Treatment Region (as randomized, see Section 5.3) Confidence intervals for the rate per 100 person-years will also be reported. For within-group rates, the two-sided 95% CI will be obtained using an exact Poisson method. For difference in rates between treatments, the two-sided 95% CI will be constructed with a Normal approximation using Wald's method [Liu, 2006]. Analysis will include only those efficacy endpoints occurring within the time period for treatment discontinuation. Calculation of time-to-event or censoring is described in further detail in Section 10.6.3. Time to stopping study medication due to meeting rescue criteria is defined as the time from Randomization until the date on which a participant permanently stops study medication due to meeting criteria for rescue. |
| Model Results Presentation |

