If the AE onset date/AE worsening and/or resolution date is missing or incomplete in the database for any occurrence of the specific AE, time to first onset/worsening and/or duration of the first, second, and third occurrence will be left missing for the participant. These summaries of special interest AEs will be provided for those AEs classified as treatment emergent.

Adverse Events

The number, percentage, and exposure-adjusted AE incidence rate per 100 person-years of participants reporting at least one AE will be provided for each treatment group. These events will be summarized by treatment group, primary system organ class, and preferred term. Similarly, the number and percentage of participants reporting at least one follow-up AE will be summarized by treatment group, primary system organ class, and preferred term.

In addition, all treatment emergent AEs will be summarized by treatment group, primary system organ class, higher level term and preferred term. In addition to generating number and percentage of subjects with treatment emergent SAEs, relative risk and 95% Wald confidence intervals will be presented for each HLT and PT as described in Section [10.6.4](#).

Summaries of all treatment emergent AEs will be produced for the following subgroups - age group, gender, race group, and weight quartile- by treatment group, primary system organ class, and preferred term.

A listing of AE records for all participants who reported AEs will be produced.

The number and percentage of participants reporting the most common treatment emergent AEs (those occurring in $\geq 5\%$ of participants in any treatment group) will be summarized by preferred term and treatment group.

The number and percentage of participants reporting treatment emergent AEs assessed by the investigator to be related to the study drug (termed as drug-related hereafter) will be summarized by treatment group, primary system organ class, and preferred term.

The number and percentage of participants reporting treatment emergent AEs by maximum intensity will be summarized by treatment group, primary system organ class, and preferred term.

The number and percentage of participants reporting treatment emergent drug-related AEs by maximum intensity will be summarized by treatment group, primary system organ class, and preferred term.

A listing of which participants reported specific adverse events will be produced.

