10.4.2. Treatment Emergent Flag for Adverse Events

All AEs (non-serious AEs and serious AEs) will be collected and recorded on the eCRF from the start of treatment until the follow-up visit at the time points specified in the SoA from [Appendix 10](#). Serious AEs assessed as related to study participation (e.g., study treatment, protocol-mandated procedures, invasive tests, or change in existing therapy) or related to a GSK product will be recorded on the eCRF from the time a participant consents to participate in the study up to and including any follow-up contact.

| Treatment State | Definition |
|---|--|
| Pre-treatment | 
 For participants with a non-missing screen failure date, if AE onset is on or before the screen failure date: AE Start Date \leq Screen Failure Date For randomized participants with a missing treatment start date, all AEs are considered pre-treatment For randomized participants with a non-missing treatment start date, if AE onset date is before treatment start date: AE Start Date $<$ Treatment Start Date |
| Post-randomization | If AE onset date or AE worsening date is on or after the randomization date Randomization date \leq AE Start Date Randomization date \leq AE Worsening Date |
| Treatment emergent | If AE onset date or AE worsening date is on or after treatment start date & on or before the last non-zero dose date plus 1 day. Treatment Start Date \leq AE Start Date \leq Last Non-Zero Dose Date + 1 day Treatment Start Date \leq AE Worsening Date \leq Last Non-Zero Dose Date + 1 day |
| Follow-up | If AE onset date or AE worsening date is after the last non-zero dose date plus 1 day. AE Start Date $>$ Last Non-Zero Dose Date + 1 day AE Worsening Date $>$ Last Non-Zero Dose Date + 1 day |
| Onset /Worsening Time Since 1 st Dose (Days) | If Treatment Start Date $>$ AE Onset Date = AE Onset Date - Treatment Start Date If Treatment Start Date \leq AE Onset Date = AE Onset Date - Treatment Start Date + 1 If Treatment Start Date $>$ AE Worsening Date = AE Worsening Date - Treatment Start Date If Treatment Start Date \leq AE Worsening Date = AE Worsening Date - Treatment Start Date + 1 Missing otherwise. |

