| 
 ● Relative risk and 95% confidence interval will be calculated as follows: Relative Risk (RR) = pd / pc Lower limit of 95% CI = $RR * \exp[-z * (v)^{1/2}]$ Upper limit of 95% CI = $RR * \exp[z * (v)^{1/2}]$, where $v = \text{Variance}[\ln(RR)] = [(1-pc) / nc1] + [(1-pd) / nd1]$ nc : number of subjects in placebo group nd : number of subjects in daprodustat group nc1 : number of subjects with AE in placebo group nd1 : number of subjects with AE in daprodustat group pc : proportion of subjects with AE in placebo group = $nc1 / nc$ pd : proportion of subjects with AE in daprodustat group = $nd1 / nd$ 
 ● z : 97.5th percentile of the standard normal distribution |

Order of CV Safety Endpoint Events

- If multiple events occur on the same day or have imputed dates that place them on the same day, but it is not clear which event occurred first, then the following order will be applied:
 1. MI
 2. Stroke
 3. Hospitalization for Heart Failure

CONFIDENTIAL

205270

Order of CV Safety Endpoint Events

4. Thromboembolic Event: DVT
5. Thromboembolic Event: VAT
6. Thromboembolic Event: PE
7. Death

Laboratory Parameters

- If a laboratory value which is expected to have a numeric value for summary purposes, has a non-detectable level reported in the database, where the numeric value is missing, but typically a character value starting with '<x' or '>x' (or indicated as less than x or greater than x in the comment field) is present, the number of significant digits in the observed values will be used to determine how much to add or subtract in order to impute the corresponding numeric value.
 - Example 1: 2 Significant Digits = '< x' becomes $x - 0.01$
 - Example 2: 1 Significant Digit = '> x' becomes $x + 0.1$
 - Example 3: 0 Significant Digits = '< x' becomes $x - 1$
- If a laboratory value which is expected to have a numeric value for summary purposes, has a non-detectable level reported in the database, where the numeric value is missing, but typically a character value starting with '≤x' or '≥x' is present, then the corresponding numeric value will be set equal to x.
- If there is more than one laboratory value on the same date for the same laboratory test, then the laboratory values associated with scheduled visits will be used.
- The following will be used to convert laboratory values from SI units to conventional units [Iverson, 2007]:

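### The only adverse-event contrast with a confidence interval divides crude proportions over an on-treatment window that rescue can shorten; Tables 3.2 and 3.22 should add an exposure-adjusted contrast

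*SAP*

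**What the plan says.** SAP 8.2 (Adverse Events Analyses) states that "relative risk and 95% Wald confidence intervals will be presented for each HLT and PT". The displays are Table 3.2, "Summary of All Treatment Emergent Adverse Events by System Organ Class, Higher Level Term, and Preferred Term", and Table 3.22, "Summary of Serious Treatment Emergent Adverse Events by System Organ Class, Higher Level Term, and Preferred Term". The Table 3.2 row does not itself mention an RR. The link is the SAP 8.2 paragraph on all treatment-emergent events, whose RR sentence refers to SAEs; the serious-event paragraph makes the same statement for Table 3.22 directly.

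SAP 10.6.4 defines the RR as pd/pc, where pd is the "proportion of subjects with AE in daprodustat group" (nd1/nd) and pc is the "proportion of subjects with AE in placebo group" (nc1/nc). Neither contains a time term.

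SAP 10.4.2 counts an event as treatment emergent if it starts or worsens on or after treatment start and "on or before the last non-zero dose date plus 1 day". Protocol 7.7.2 (Table 7) evaluates rescue from Week 4 and says of a rescued participant: "Randomized treatment should be permanently discontinued (but participant should remain in study to monitor Hgb". Protocol 8.1 lists meeting rescue criteria among the mandatory reasons for stopping study treatment.

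Exposure-adjusted rates for both arms are specified in Tables 3.1, 3.16, 3.24, 3.44 and 3.45, but not in Tables 3.2 and 3.22. No between-arm rate contrast is specified for adverse events. For time to rescue, SAP 7.3.2.1 does specify one: "For difference in rates between treatments, the two-sided 95% CI will be constructed with a Normal approximation using Wald's method".

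**The concern.** A participant who stops for rescue stays in the RR denominator, but any later event drops out of the numerator. If rescue is more frequent on placebo, placebo participants have less time in which an event can be counted, and the crude RR mixes any effect on adverse events with a difference in observation time.

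The sponsor has reason to expect such a difference. Rescue is triggered by low hemoglobin, the design assumes a 1.0 g/dL difference between arms (Protocol 10.2.1), and time to stopping for rescue is tested for superiority of daprodustat (SAP 7.3.2.1). Greater efficacy would then push the crude ratios up. These are the ratios that come with an interval, so readers are likely to look to them for safety signals.

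**Working it through.** The documents state no expected adverse-event RR and no rescue rate by arm, so there is no planned figure to reproduce.

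**Inputs from the documents.** Treatment period 28 weeks; rescue evaluated from Week 4; 300 participants per arm; hemoglobin difference 1.0 g/dL with SD 1.5 g/dL; 30% of placebo participants with a rise of at least 1.0 g/dL (Protocol 5.1, 7.7.2, 10.2.1).

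**Assumptions.** The same constant event hazard h per week in both arms; a fraction r of an arm stops for rescue, at times uniform over Weeks 4-28 (sensitivity: Weeks 4-16).

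**Plausible rescue fractions.** The 30% figure implies a mean placebo change of 1.0 - 0.524 × 1.5 = 0.21 g/dL, hence 1.21 g/dL on daprodustat. With an assumed baseline of 9.3 g/dL and a normal distribution:
- P(Hgb < 7.5) is 9.0% on placebo and 2.2% on daprodustat.
- P(Hgb < 8.5) is 25% and 9%.

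These only anchor the range; they are not predictions.

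**Formulas.** Mean window = (1 - r) × 28 + r × 16 weeks (r × 10 for early stops). Risk = (1 - r)(1 - e^(-28h)) + r × the average of (1 - e^(-ht)) over stop times t. Expected RR = risk on daprodustat / risk on placebo. For uncommon events this is close to the ratio of mean windows; for example 27.76/26.92 = 1.031.

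| Rescue, placebo v daprodustat | Mean window, weeks | Expected RR, stops Weeks 4-28 | Expected RR, stops Weeks 4-16 |
|---|---|---|---|
| 5% v 1% | 27.40 v 27.88 | 1.017 | 1.026 |
| 9% v 2% | 26.92 v 27.76 | 1.031 | 1.047 |
| 10% v 2% | 26.80 v 27.76 | 1.035 | 1.054 |
| 25% v 9% | 25.00 v 26.92 | 1.076 | 1.121 |
| 30% v 5% | 24.40 v 27.40 | 1.121 | 1.197 |

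The RR columns use a background risk of 5% over 28 weeks. At 50% the shift is smaller (9% v 2%: 1.026; 30% v 5%: 1.103).

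**Limits of the effect.**
- Equal rescue in both arms (10% v 10%) gives 1.000.
- Events confined to the time before Week 4 give 1.000.
- If 10% of daprodustat participants end on an 8-week dose hold, their arm loses 0.8 weeks on average. The 9% v 2% case becomes (27.76 - 0.8)/26.92 = 1.001, and the 25% v 9% case (26.92 - 0.8)/25.00 = 1.045.
- For an event with 3% risk and 300 per arm, the simulated RR is above 1 in 48% of trials and below 1 in 43% (9% v 2%), or 55% and 36% (30% v 5%).

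**Effect on the interval.** For rescue of 10% v 2%, 20% v 5% and 30% v 5%, the SAP's Wald interval lies wholly above 1, with no true effect on events, in about:
- 2.7%, 3.2% and 4.3% of trials for an event in 5% of participants (2.2% with no rescue);
- 3.3%, 4.3% and 6.3% for one in about 10%;
- 5%, 9% and 17% for one in about 40%.

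The nominal value is 2.5%. The effect matters mainly for common terms and groupings.

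**With person-time in the denominator.** Expected events divided by time at risk equals h in each arm, so the expected rate ratio is 1.00 whatever the rescue fractions.

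**The case against.** Several points against the concern are sound.

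- **Rescue rates are not documented.** Protocol 5.4 expects few drop-outs for lack of effect and notes that such patients can maintain or even raise their hemoglobin. A shorter placebo window is an inference.
- **There is an opposing force.** Counting ends at the last non-zero dose, and SAP 10.6.1 recognises that a participant on hold can complete the study without taking treatment. Holds for high hemoglobin would be expected mainly on daprodustat. Which force prevails is unknown in advance.
- **Much is already reported.** Table 3.1 (all treatment-emergent events) and Table 3.44 (serious events) give exposure-adjusted rates by preferred term for both arms. Follow-up events appear in Tables 3.3 and 3.23, exposure by arm in Table 1.18, and the MACE tables use the ITT population.
- **Nothing confirmatory depends on these intervals.** Protocol 10.4.2.2 makes the safety analysis descriptive.

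These points limit the size and importance of the concern but leave one gap: single-arm rates show a direction by preferred term, without an interval and without anything at higher-level-term level.

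A reader might infer more than the documents support. It is tempting to say that an inert drug would show an RR above 1, but such a drug would not change rescue and the expected RR would be 1. It is also tempting to say that every term is shifted, or that harm cannot be told apart from longer observation. Events before Week 4 are unaffected, observed ratios scatter on both sides of 1, and Tables 3.1 and 3.44 allow a check by preferred term.

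**Conclusion.** The point holds as a modest, conditional bias and an inexpensive improvement. The condition is a drug that reduces rescue through hemoglobin while leaving adverse events unchanged. The expected crude RR for events that can arise after Week 4 is then about 1.02-1.12 over the assumed rescue fractions, and at most about 1.20 with early stops and the widest gap considered. The figures rest on a constant and equal event hazard, assumed stop times and assumed rescue fractions, and they ignore terminal holds except where shown. Because the net direction cannot be fixed beforehand, the case is for a contrast that handles unequal time at risk either way, not for presuming a bias against daprodustat.

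**What to change.** In Tables 3.2 and 3.22, keep the crude RR and add, at higher-level-term and preferred-term level, an exposure-adjusted incidence rate difference (or ratio) with a 95% CI. The rate-difference method already cited for time to rescue in SAP 7.3.2.1 can be used.

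The SAP should also say which person-time applies, because 10.6.4 contains two definitions. The AE participant-years definition runs from treatment start to the first event or, without an event, to the last non-zero dose plus one day (the last non-zero dose date itself for those not continuing on study past that day). That matches the counting window. The exposure-adjusted incidence formula runs instead to the treatment stop date, so time on a terminal hold would enter the denominator while its events go uncounted. In the hold example with 9% v 2% rescue, the daprodustat rate would be understated by a factor of (27.76 - 0.8)/27.76 = 0.97. The participant-years definition should be used.

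The cost is a few lines of SAP text and a computed estimate with its interval in two tables. The downside is that a rate contrast assumes a roughly constant hazard and describes early-onset events less well, which is a reason to keep the crude RR alongside. The tables remain descriptive.
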